7.3. Exclusion Criteria

A potential patient will be excluded from the study if any of the following criteria apply:

- 1. INR ≥1.2 at Screening (one retest permitted). If based on opinion of Investigator and/or prescribing physician patient is appropriate for anticoagulant holiday, patient may stop taking anticoagulant for an appropriate washout period and if indicated a repeat INR within <1.2 would be acceptable. Vitamin K may be used for reversal. If INR is not indicated (direct thrombin inhibitors or Xa inhibitors) then appropriate washout period alone may be acceptable. (Note: Anti-platelet agents, aspirin, clopidogrel or nonsteroidal anti-inflammatory drugs [NSAIDs] are acceptable but must be held 7 days before and 7 days after liver biopsy)
- 2. Platelet count $<150 \times 10^9/L$ at Screening (one retest permitted)
- 3. ALT and AST levels >250 U/L at Screening (one retest permitted)
- 4. Estimated glomerular filtration rate (eGFR) <60 mL/min/1.73m² at Screening (one retest permitted)
- 5. FEV₁ <65% of predicted (preferentially post-bronchodilatory reading) at Screening (one retest permitted)
- 6. Recent (last 3 months) pneumonia or lower respiratory infection (which must be verifiable from the medical record). Patient reported infection is not sufficient to meet this criterion.
- 7. Unavoidable exposure to inhaled environmental toxins that in the clinical judgment of the Investigator could impair pulmonary function significantly over the course of the study.

- 8. Human immunodeficiency virus (HIV) infection, as shown by the presence of anti-HIV antibody (sero-positive)
- 9. Seropositive for HBV (HBsAg positive at Screening) or HCV (detectable HCV RNA at Screening). Cured HCV (positive antibody test without detectable HCV RNA is acceptable).
- 10. Uncontrolled hypertension (Systolic BP >170 and diastolic blood pressure [BP] >100 mmHg at Screening). Patients may rescreen once BP is successfully controlled.
- 11. A history of torsades de pointes, ventricular rhythm disturbances (e.g., ventricular tachycardia or fibrillation), untreated heart block (excluding first-degree block, being PR interval prolongation only), congenital long QT syndrome or new acute ST segment elevation or depression or new acute Q wave on ECG. Stable atrial dysrhythmias (e.g., stable atrial fibrillation) are acceptable.
- 12. Symptomatic heart failure (per New York Heart Association guidelines), unstable angina, myocardial infarction, severe cardiovascular disease (ejection fraction <20%), transient ischemic attack (TIA) or cerebrovascular accident (CVA) within 6 months prior to Screening
- 13. History of malignancy within the last 1 year except for adequately treated basal cell carcinoma, squamous cell skin cancer, superficial bladder tumors, or in situ cervical cancer. Patients with other curatively treated malignancies who have no evidence of metastatic disease and >1-year disease-free interval may be entered following approval by the Medical Monitor
- 14. History of major surgery within the prior 1 month prior to Screening
- 15. Regular use of alcohol within one month prior to the Screening visit (i.e., more than 14 units of alcohol per week [1 unit = 150 mL of wine, 360 mL of beer, or 45 mL of 40% alcohol])
- 16. Use of illicit drugs (such as cocaine, phencyclidine [PCP]) within 1 year prior to the Screening visit or positive urine drug screen at Screening (a urine drug screen positive for benzodiazepines, opioids or tetrahydrocannabinol is acceptable for enrollment at the discretion of the Investigator). The patient may still be eligible at discretion of Medical Monitor and Investigator if positive urine drug screen is due to a prescription medication.
- 17. Use of an investigational agent or device within 30 days prior to dosing or current participation in an investigational study involving a therapeutic intervention. Patients who have participated in the ARCAAT-1001 study or observational studies are acceptable. Patients previously enrolled in but no longer enrolled in gene therapy studies are acceptable. Patients receiving AAT augmentation therapy as part of a post-marketing study or other access program for approved therapies are acceptable.
- 18. Blood donation (≥500 mL) within 7 days prior to study treatment administration.

- 19. Any concomitant medical or psychiatric condition or social situation that would make it difficult to comply with protocol requirements or put the patient at additional safety risk. Patients with NASH, NAFLD, metabolic syndrome, well controlled diabetes mellitus (even if on insulin) or hemochromatosis are acceptable if disease is stable and does not pose a significant threat to patient participation. Patients enrolled with NASH should have no plans to undergo bariatric surgery or have initiated or plan to initiate pharmaceutical therapy for NASH (such as Vitamin E or pioglitazone) during the course of the study.
- 20. A history of thromboembolic disease (including deep vein thrombosis or pulmonary embolism), myocardial infarction, stroke within three (3) months of Screening.
- 21. Any other condition or finding of clinical relevance at Screening that, in the opinion of the Investigator, would render the patient unsuitable for enrollment or could interfere with participating in and completing the study.
- 22. Previous diagnosis of definitive liver cirrhosis based on biopsy or complications of cirrhosis (e.g., varices, ascites, hepatic encephalopathy) based on source verifiable medical record.
- 23. Patients who have undergone lung or liver transplant for AATD are excluded.

Note: Sponsor Medical Monitor has the option to exclude the enrollment of a patient if, based upon the patient's medical history or Screening results, it is felt that a patient's safety may be at risk.

* All laboratory tests used as exclusion criteria may be repeated once, and the repeat value may be used for exclusion purposes.

7.4. Patient Withdrawal Criteria

Patients will be advised that they are free to withdraw from the study at any time for any reason or, if necessary, the Investigator, or medically trained designee, may withdraw a patient from the study, per the following criteria, to protect the patient's health:

- the need to take medication which may interfere with study measurements
- intolerable/unacceptable adverse experiences
- major violation of or deviation from study protocol procedures
- noncompliance of patient with protocol
- patient unwilling to proceed and/or consent is withdrawn or
- withdrawal from the study if, in the Investigator's judgment, it is in the patient's best interest

pregnancy

The reasons for withdrawal will be recorded on the electronic case report form (eCRF) and included in the final clinical study report, along with any AEs and any necessary medical treatment.

If a patient is withdrawn from the study due to significant AE or SAE, the Investigator, or medically trained designee, will evaluate the urgency of the event. If the situation warrants, the Investigator, or medically trained designee, will take appropriate diagnostic and therapeutic measures. If the situation is not an immediate emergency, the Investigator, or medically trained designee, at the clinical study facility will attempt to contact the study's Medical Monitor or medically qualified designee for consultation. No medical help, diagnosis, or advice will be withheld from the patient due to an inability to contact the Medical Monitor. The patient will be encouraged to remain available for follow-up medical monitoring. The Sponsor will be notified as soon as possible of any patient withdrawals.

Patients who are withdrawn or discontinue prior to EOS visit, will not be replaced.

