Any discontinued patient will be followed with appropriate assessments and monitoring (either per SOA or with more intensive evaluation) through EOS. Sponsor or Investigator can discontinue any patient at any time with or without DSMB consultation. If such events (as described in #1 through #3 above) occur and the patient is not discontinued from the study, the reason for not discontinuing the patient will be included in DSMB meeting minutes. Including, but not limited to the events listed above, the DSMB may pause the study to additional dosing to provide time to evaluate safety data and recommend the action to be taken, which may include, but is not limited to, one of the following:

- Discontinuation of a patient or group of patients from the study
- The study is stopped immediately with no further dosing
- The study will continue, but using a lower dose
- The study will continue as planned

Arrowhead will notify the concerned regulatory agencies and ethics committees immediately and at least within 15 days from when the trial is temporarily halted or prematurely discontinued. A substantial protocol amendment will be submitted to the concerned regulatory agencies clearly explaining the reasons and scope, e.g., stopping recruitment and/or interrupting treatment of all patients already included. Furthermore, to restart the trial, the request will be submitted in form of a substantial amendment providing evidence that it is safe to restart the trial. If Arrowhead decides not to recommence a temporarily halted trial, the concerned regulatory agency(-ies) will be notified within 15 days of this decision, providing a brief explanation of the reasons for ending the trial.

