11.10. Analysis Methods

The primary objective of the study is to evaluate the 3 doses of fazirsiran versus placebo and select a single active dose to be evaluated further in later stage studies and used in the open-label phase of this study. In addition to examination of safety, dose selection will be based on the evaluation of the mean percent change from baseline (Day 1, pre-dose) in serum Z-AAT levels through Week 16. The primary efficacy analysis, executed after all enrolled patients reach the Week 16 evaluation, will be performed using a MMRM approach. The repeated measures of the response are the values obtained at the scheduled study Weeks 2, 4, 6, and 16. The model will include fixed categorical effects for treatment, time, week, treatment by week interaction, and a baseline value of serum Z-AAT as a continuous covariate. Restricted maximum likelihood estimation (REML) with an unstructured within-patient covariance structure will be used. If the model fails to converge, alternative covariance structures will be considered.

Based on the stated model, least squares (LS) estimates of the mean percent change from baseline for each treatment group, of the difference for each fazirsiran dose group and pooled placebo, and the corresponding 95% CIs will be reported for each timepoint. P-values from the Week 16 2-sided t-tests of each for each of the 3 dose groups vs placebo group will be evaluated for significance using Hochberg's step-up procedure to adjust for multiplicity of testing. Placebo group will be pooled from placebo patients in 3 dose cohorts. The primary evaluation of interest is at Week 16 timepoint, to be completed in all randomized patients who receive at least one dose

of study treatment (FAS), regardless of the total number of received doses or any intercurrent events (hypothetical estimand).

Secondary endpoints include:

- Subject incidence of treatment-emergent AEs
- Absolute and percent change from baseline in total liver Z-AAT (insoluble + soluble) protein at post-dose biopsy
- Absolute and percent change from baseline in liver Z-AAT soluble protein at postdose biopsy
- Absolute and percent change from baseline in liver Z-AAT insoluble protein at post-dose biopsy
- Absolute and percent change from baseline in liver function tests, including ALT, AST, ALP, GGT, total bilirubin, direct bilirubin and INR at Week 16 and over time through EOS
- Absolute and percent change in serum Z-AAT overtime through EOS

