If cirrhosis is detected on liver biopsy the patient will be discontinued from treatment and followed through EOS per SOA. This biopsy will represent EOS biopsy for purposes of endpoint determination. If cirrhosis is not confirmed on liver biopsy, patient may continue on treatment.

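### Section 7.4 lets patients be withdrawn from the study, not only from treatment, for interfering medication, deviation or noncompliance; this must be reconciled with Section 6.3 and Appendix 2.

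*Protocol*

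**What the plan says.** Protocol Section 7.4 states that the investigator, if necessary and to protect the patient's health, "may withdraw a patient from the study, per the following criteria". Three of the listed grounds concern the data or study conduct: "the need to take medication which may interfere with study measurements", "major violation of or deviation from study protocol procedures" and "noncompliance of patient with protocol". The same list covers intolerable adverse experiences, pregnancy, the patient's best interest and withdrawn consent. Withdrawn patients are not replaced. The only reference to continued contact is that a patient withdrawn for a significant adverse event is encouraged to remain available for medical monitoring.

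Section 6.3 says: "Any discontinued patient will be followed with appropriate assessments and monitoring (either per SOA or with more intensive evaluation) through EOS". Appendix 2 follows the same principle: "If cirrhosis is detected on liver biopsy the patient will be discontinued from treatment and followed through EOS per SOA". It also says that a patient whose liver enzymes rise again on rechallenge stops drug and is followed in the study.

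Under Section 9.3.11, a patient whose participation ends has one Early Termination visit within 30 days of the decision. The supplied SAP is an addendum on open-label summaries. It refers to SAPv3.0, which was not supplied, for most definitions, and does not address the point.

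**The concern.** None of the three data-related grounds requires follow-up to end. A patient who takes a medication that disturbs an assay, misses procedures or breaks a rule can still attend visits, and most of the safety and liver data would still be informative. A site that applies 7.4 as written can nevertheless close the patient out after one visit, while a site that reads 6.3 as governing would keep the patient to EOS.

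These grounds may be related to treatment or outcome. A patient may need new medication because the disease has changed, or comply poorly because of tolerability. Section 11.10 says that continuous secondary endpoints are analysed in a similar way to the primary, with a repeated-measures mixed model for longitudinal measures. Section 11.10 states the missing-at-random assumption for that model in the primary analysis, and describes its control-based sensitivity analysis for the primary endpoint only. For later endpoints it is better to avoid the gap than to model it. With arms this small, each patient counts.

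**Working it through.** **1. The passages side by side**

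| Place | What stops | Follow-up afterwards |
|---|---|---|
| 7.4, the three data-related grounds | Study participation | None beyond the Early Termination visit (9.3.11) |
| 6.3, any discontinued patient | Not stated whether treatment or study | Through EOS |
| Appendix 2, cirrhosis on biopsy | Treatment | Through EOS |
| Appendix 2, recurrence on rechallenge | Treatment | Followed in the study |

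The protocol already has the category of being off treatment and on study, but 7.4 does not use it. If the 6.3 sentence covers 7.4 withdrawals, the two conflict on whether visits continue. If it covers only stopping-rule cases, 7.4 leaves follow-up unaddressed. Either way the text needs one answer.

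**2. What is no longer exposed**

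Sections 6.1 and 11.11 state that all enrolled patients had completed Week 16 when the interim analysis was done. Later withdrawals cannot remove the primary endpoint.

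Power is not the issue either. Section 11.2 assumes 8 patients per active group, 12 on pooled placebo, a difference of 70 percentage points, SD 35, and one-sided 2.5% with Hochberg's procedure. It states 99% power for at least one dose and 97% for all doses. Simulating 400,000 trials with a pooled variance gives 99.8% and 97.0%, so the stated figures reproduce. Under assumed losses (the documents give no rate):

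- 7/7/7 against 11: 99.5% and 94.5%
- 6/6/6 against 9: 98.3% and 88.5%

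**3. What remains exposed**

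- *Biopsy timing.* For patients with fibrosis the post-dose biopsy is set at Week 48, or at Week 72 or 96 for those already past Week 48 when Protocol v4.0 was approved. The Early Termination column of Table 2 includes a biopsy unless one was already done, and Sections 11.8 and 11.10 allow it to serve as the post-dose biopsy. Tissue is therefore not necessarily lost, but it may be taken after a shorter exposure. Section 6.2 expects liver changes to need six months or more.
- *Later serum and liver endpoints* followed through EOS.
- *Long-term safety*, including pulmonary function and time to augmentation therapy (9.7), and the open-label phase, whose stated purpose in 6.2 is long-term safety.

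**4. Scale of one withdrawal before the biopsy**

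Inputs: at least 24 of about 36 patients have fibrosis (7.1), with 2:1 allocation in three cohorts (11.3). Assumption: patients with fibrosis are spread evenly. Fibrosis is not a stratification factor.

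- Minimum of 24: active 24 × 2/3 ÷ 3 = 5.33 per dose; placebo 24 × 1/3 = 8. One patient is 1/5.33 = 18.8% of an active arm or 1/8 = 12.5% of placebo.
- Upper bound, all 36 with fibrosis: active 36 × 2/3 ÷ 3 = 8; placebo 12. One patient is 1/8 = 12.5% or 1/12 = 8.3%.

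These are shares of biopsies taken on schedule, not of analysable biopsies.

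**The case against.** The strongest case against is that 7.4 is permissive, applies only if necessary, and is framed around the patient's health. The Early Termination visit collects serum Z-AAT, laboratory tests, lung function, imaging and, for patients with fibrosis, a biopsy. The 6.3 sentence also sits among the DSMB and stopping rules, so it may not have been written with 7.4 in mind. All of this stands, and it limits the size of the point. It does not tell a site whether visits continue, and discretion without a default invites different practice between sites.

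Three stronger readings are tempting, and the documents do not support them.

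- *Patients whose lungs worsen would be withdrawn for starting new medication.* Sections 7.5 and 9.3.9 permit augmentation therapy and standard COPD treatment. Appendix 3 keeps such patients on study with spirometry about monthly and DSMB review. Lung decline leads to more data, not less.
- *The analysis promises data to EOS because it runs "regardless of the total number of received doses or any intercurrent events".* That phrase in 11.10 describes the Week 16 evaluation, which is complete. It says nothing about biopsy or open-label data.
- *Two withdrawals out of 36 (5.6%) breach a missing-data limit.* The 5% figure in 11.10 triggers a control-based sensitivity analysis of the primary endpoint. It is not a tolerance for later data, and a tipping-point analysis is planned as well.

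A reader might also conclude that study withdrawal should be confined to withdrawn consent, loss to follow-up or death, with everyone else kept for the scheduled biopsy. That would override the investigator's discretion on pregnancy, adverse events and best interest, and could require an invasive procedure of those patients. The inconsistency does not justify it.

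**Conclusion.** The inconsistency is real and modest. For interfering medication, deviation and noncompliance, 7.4 ends study participation where 6.3 and Appendix 2 point to continued follow-up. At risk are biopsy timing, post-Week 16 serum and liver endpoints, and long-term safety data. The primary result and its power are not at risk.

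One early withdrawal would replace with an off-schedule biopsy, or lose, roughly one of about 5 scheduled biopsies in an active arm. This assumes the minimum of 24 patients with fibrosis and even allocation; with more such patients the share is smaller. How many withdrawals of this kind to expect cannot be said, because the documents give no rate. SAPv3.0 might define the terms more closely, but it cannot make a site continue visits that the protocol allows it to end.

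**What to change.** In Section 7.4, state that for the three data-related grounds (interfering medication, deviation, noncompliance) a patient whose treatment stops remains in the study and is followed through EOS with appropriate assessments, as in 6.3, unless consent is withdrawn. Cross-refer 7.4 to 6.3 and Appendix 2 so that all three use the same terms for stopping treatment and leaving the study. Say how interfering medication relates to the therapies that 7.5 permits.

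Leave unchanged the grounds for stopping treatment and the investigator's discretion on safety, pregnancy and whether any biopsy is done.

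The cost is a wording change and the completion, for a few more patients, of visits already in the schedule of assessments.

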7.5. Restrictions and Concomitant Medications

- 1. **Study Visit Duration:** For each patient, clinic visits will last approximately 4 hours on dosing days. Patients will return to the clinical facility for outpatient visits as per the SOA. Patients will be observed post-dose for approximately 2 hours or as clinically indicated as per the Investigator.
- 2. *Fasting:* On the day of dosing, patients will fast from food for at least 2 hours prior to study treatment administration. Fasting requirements prior to assessments include:
 - a. Blood collection for study labs: patients should fast for a minimum of 2 hours (water only)
 - b. MRI/magnetic resonance elastography (MRE): fast for a minimum of 4 hours
 - c. Liver Biopsy: fast for a minimum of 6 hours
- 3. **Recreational Drugs, Smoking, and Alcohol:** Patients will be instructed to abstain from consuming alcohol for at least 48 hours prior to their clinic visit on dosing days, and during the clinic visit. In addition, Patients will be instructed to refrain from regular use of alcohol (i.e., more than 14 units of alcohol per week [1 unit = 150 mL of wine, 360 mL of beer, or 45 mL of 40% alcohol]) for the study duration. Patients must abstain from use of recreational drugs throughout the study. Patients must be non-smokers entering the study (as per Inclusion and Exclusion criteria) and abstain from smoking tobacco (including e-cigarettes) for the duration of the study. Nicotine patches or gum is acceptable.
- 4. *Concomitant Medications*: Allowance of concomitant medications will be at the discretion of the study Investigator in consultation with the study's Medical Monitor (when necessary). Augmentation therapy is permitted. Procedural sedation with benzodiazepines or equivalent during MRI or liver biopsy as needed is permitted.

Standard of care for chronic obstructive pulmonary disease (COPD) including bronchodilators, corticosteroids, and other modalities are permitted.

8. INVESTIGATIONAL PRODUCT

8.1. Description, Identification and Dosage

Arrowhead Pharmaceuticals, Inc. is responsible for the supply of Fazirsiran Injection together with detailed instructions (in a Pharmacy Manual) describing preparation of Fazirsiran (TAK-999, ARO-AAT) Injection. The PBO (normal saline 0.9%) will be supplied by the clinical site.

Accordingly, Fazirsiran Injection will be supplied as single sterile 2-mL vial containing the active pharmaceutical ingredient (API) fazirsiran, with the correct dose prepared by the pharmacy or designee prior to dosing patients.

The PBO will be 0.9% normal saline (supplied by the clinical site) administered subcutaneously.

Doses administered per Dose Level:

Each single dose of either active drug (fazirsiran) or PBO (normal saline 0.9%), will be administered by subcutaneous injection. Injections will be made into the subcutaneous tissue at an appropriate site (e.g., abdomen, thigh, upper arm, etc.) using a 25 to 30 gauge, ½ inch needle. The abdomen is the preferred site. The injection site is to be varied (no multiple injections into the same exact site, and alternating various locations on the abdomen is acceptable) and injection site location is to be recorded in the eCRF. Prior to dose administration, the Fazirsiran Injection vial must be allowed sufficient time to come to room temperature. Do not inject into areas of active skin disease or injury such as sunburns, skin rashes, inflammation, or skin infections. Injection volume per injection site should not exceed approximately 1.0 mL. There will be no dose escalation within a cohort (i.e., the same drug dose will be administered to each patient within a cohort). The randomization schedule will be provided to each clinical site and will be maintained along with any other materials that could jeopardize the blind in a secured area of the pharmacy.

